10.5 IRB/EC Approval

Institutional Review Board (IRB)/Ethics Committee (EC) approval will be obtained prior to conducting this study. Sequentially, all consecutive patients will be offered study enrollment at each study site to avoid potential selection bias. All potential subjects will be required to participate in an informed consent process and sign the IRB/EC approved written informed consent prior to study enrollment. Once Informed Consent has been obtained, eligibility will be determined and preoperative study data collected via direct interview with the patient. Study data cannot be collected until the candidate has completed the informed consent process and signed and dated the IRB/EC approved Informed Consent.

10.6 Type and Timing of Observations

This study is designed to be prospective to ensure that the study population is representative of the type of population that the device is intended to treat. To reduce bias, a consecutive subject series will be recruited. After the initial visit followed by the surgery, the subject is expected to participate in the study for a time period of 2 years. Subjects will be enrolled during a period of 24 months, and the study will last until complete collection of the 2-year follow-up data. All subjects will undergo pre-operative, intra-operative and post-operative assessments including physical examinations and collection of quality-of-life metrics. The visit intervals will be pre-op, operative, 2 weeks, 6 weeks (± 7 days); 1 and 2 years (± 90 days).

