10.7.1 Primary Endpoint

The primary endpoint is defined by the overall group mean improvement from baseline of the Modified Harris Hip Score at the two year time point. The safety of the system will be assessed by monitoring the frequency and incidence of adverse events. Relation of the events to implant (Accufill®), instrumentation (SCP® Surgical Instrumentation) and/or procedure should be specified.

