11.7 Follow-up Procedures

In order to minimize the burden to patient and physician, patients will be enrolled at the physician's office, but will not be required to come back to the office for follow-up visits.

A Numeric Pain Score will be collected at the first post-operative standard of care visit at approximately 7-21 days.

Thereafter, subjects complete self-reported outcomes measures post-operatively at 6 weeks, 12 weeks, 6 months, 1 year and 2 years. These measures include:

- Use of pain medication and therapy
- Subject-reported outcomes:
 - Numeric Pain Scale
 - Modified Harris Hip Score
 - Hip Outcome Score
 - EQ-5D
 - Subject Global Satisfaction Survey

The post-operative visit data must be collected for each enrolled subject via email, in-person, regular mail or telephone (with an IRB approved phone script). If the subject is not seen in person, a member of the study staff will contact the subject by telephone at the aforementioned time points to inquire about their outcomes, any conversion surgeries, and adverse events.

Follow-up evaluations are detailed in Table 1— Schedule of Events. Follow-up is to occur within the windows described in Table 1.

The study database will be configured to send an email notification to subjects at the beginning of each specified visit window with a reminder that they need to complete the surveys. This email will contain a method to allow the subjects to complete their surveys electronically via the database's electronic Patient Reported Outcomes (ePRO) system.

Prior to contacting the study subject to assess potential adverse events by telephone, a member of the study staff will check to confirm whether these surveys have been completed electronically or not. If the subject has not completed the evaluation yet, a member of the study staff will ask if the subject would like to complete the questionnaires by phone, email or if they would like a copy of the surveys to be mailed out to them. Mailed surveys will be sent with a stamped, return envelope. The subject should be instructed to return the surveys within one week and to include the date of completion at the top of any of the pages. Any subject survey forms that are not collected via the database's ePRO system are to be maintained in the subjects' study files as source documents.

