11.8 Minimization of Loss to Follow-up

Subject follow-up is extremely important for the conduct of a clinical study. The expectation is to maintain the highest rate of follow-up compliance possible throughout this study. Subjects that are study completed as lost to follow-up will not be replaced. In an effort to minimize the number of subjects lost to follow-up, the following recommendations and/or study requirements are essential to ensure proper patient selection and compliance:

- Patient Eligibility: Subjects will be selected according to the inclusion/exclusion criteria detailed in Section 8 and are expected to return for all follow-up visits.
- Patients Counseled: Patients will be counseled during the Informed Consent process on the importance of returning for follow-up visits.
- Patient Exclusion: Patients who are not willing to return for study required follow-up visits and/or are not willing to comply with the follow-up schedule will not be considered for enrollment into the study.
- Subject Due Listings: In addition to proper patient selection, Zimmer Biomet will provide subject due notices to the sites on a regular basis in order to track each study participant and monitor adherence to the required follow-up visit timeframes. The subject due listings will facilitate scheduling the subjects for their return office visits.
- Contact Tracking: Attempts to contact subjects will be documented in the study subject's medical record. It is recommended that the first three attempts be made by telephone. If after three calls, contact has not been successful, the below is suggested prior to terminating the study subject from the study:

If	Then
a response is not received following attempts to reach the subject by phone	the Investigator could send a letter to the patient explaining the follow-up agreement per informed consent.
a response is not received from the Investigator's letter	the Investigator could use any additional contacts provided by the subject to contact the subject.
The subject missed three consecutive visits and all attempts to contact the subject are unsuccessful, or the subject is contacted and chooses to withdraw from the study	the Study Completion form may be completed and will specify the reason the patient is no longer participating in this study.

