12.4.4 Subject Withdrawal

Study participation may be discontinued through surgical conversion (Total Hip Arthroplasty or total removal of AccuFill), withdrawal of consent, Investigator decision or death. A subject may voluntarily withdraw their consent from the study at any time without prejudice or affecting their future medical treatment. Investigators may withdraw a subject due to non-compliance with the protocol or follow-up questionnaire schedule, or for reasons of medical discretion.

All consented subjects who are withdrawn/ discontinued from the study should have an End of Study form completed to explain why they are no longer participating in the study.

When a subject withdraws or is withdrawn, all study procedures completed and data collected prior to the date of withdrawal will be submitted to the sponsor and included in the study database, unless the subject requests otherwise in writing.

Should a subject who previously chose to withdraw wish to re-enter the study, a new Informed Consent will be required. The site may resume scheduled follow-up visits from the subject's last follow-up visit.

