12.4.5 Lost to Follow-up

Although follow-up compliance is essential to study quality, some subjects may not be able to complete follow-up evaluations. If the subject does not complete the required questionnaires through the two year time point and the Investigator or a member of the study staff has attempted to contact that subject at least three times (with any combination of an email reminder via EDC system, a phone call or an IRB approved subject follow-up letter) and receives no response, the subject may be deemed to be lost to follow-up. The research staff will document the attempts to contact the subject. The final attempt to contact the subject will be performed by register/return receipt mail. The receipt will be placed in the subject's binder. An End of Study/Withdrawal Form must be completed.

Should a subject expire, complete the Adverse Event and End of Study/Withdrawal Form. Submit copies of the death certificate, autopsy report (if applicable and available) and source documents related to the death. The Investigator will make written notification to the IRB upon the death of a subject in the study, based on the individual IRB requirements.

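### Subjects can be withdrawn for missed questionnaires, or closed as unreachable, well before the 2-year primary score is due; separately, section 10.6 disagrees with Table 1 and the synopsis

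*Combined protocol and SAP*

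**What the plan says.** **Endpoint.** Section 10.7.1 defines the primary endpoint as the "overall group mean improvement from baseline of the Modified Harris Hip Score at the two year time point". Section 11.7 does not require subjects to return to the office and accepts follow-up data by email, mail, telephone or in person.

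**Withdrawal.** Section 12.4.4: "Investigators may withdraw a subject due to non-compliance with the protocol or follow-up questionnaire schedule, or for reasons of medical discretion". No number of missed questionnaires is set, and failed contact is not a condition.

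**Closure.** In the contact-tracking table of section 11.8 the trigger is "The subject missed three consecutive visits and all attempts to contact the subject are unsuccessful" (or that the subject, once reached, chooses to leave). The action is that "the Study Completion form may be completed and will specify the reason the patient is no longer participating in this study". The section suggests three telephone calls, a letter and use of any additional contacts beforehand. Section 12.4.5 starts from a different condition, "If the subject does not complete the required questionnaires through the two year time point". It adds at least three contact attempts in any combination and a final registered letter, after which the subject may be considered lost. Section 11.8 also says that subjects lost to follow-up are not replaced.

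**Schedule.** Section 10.6: "The visit intervals will be pre-op, operative, 2 weeks, 6 weeks (± 7 days); 1 and 2 years (± 90 days". It lists no 12-week or 6-month visit and gives 24 months of enrolment. Table 1 has both visits and ±60 days at 1 and 2 years; the synopsis gives 5 years of enrolment. Section 11.7 says: "Follow-up is to occur within the windows described in Table 1".

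**Analysis.** Section 16 defines no analysis set, no rule for scores outside the window and no method for missing scores.

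**The concern.** A subject who misses a 6-week or 12-week form can still give a 2-year score, because that score needs only a reply to an email, letter or telephone call. Once the site has withdrawn or closed the subject, nobody asks for it. Section 12.4.4 allows this even for a subject who is reachable and has not withdrawn consent. Section 11.8 allows it for a subject who could not be reached early on but might be reached later.

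With one arm, no replacement and no missing-data method, the primary result is in effect the mean among those still in the study at 2 years. If subjects who stop answering improve less, or more, than those who keep answering, that mean is biased. Because the rules are discretionary and differ between sections, up to 15 sites may apply them differently.

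**Working it through.** **1. The plan's own sample size.** Section 16.1 assumes a mean improvement of 31.4, SD 22.4, a threshold of 18.0, alpha 0.05 and 80% power.

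- Difference: 31.4 − 18.0 = 13.4. Standardised: 13.4 / 22.4 = 0.598.
- A one-sample two-sided t-test (noncentral t) needs n = 24, with power 80.1%. This matches the plan. A one-sided test would need 19, so the plan implicitly used two sides.
- Attrition: 24 / (1 − 0.25) = 32. This also matches.

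**2. Is power at risk?** Same assumptions, about 50 enrolled:

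| Subjects with a 2-year score | Loss | Power (two-sided) |
|---|---|---|
| 50 | 0% | 98.6% |
| 37 | 26% | 94.3% |
| 24 | 52% | 80.1% |
| 23 | 54% | 78.3% |

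Power stays at or above 80% until more than about half the subjects lack a score.

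**3. How early can closure come?**

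- Section 12.4.4: no minimum time or number of missed forms is stated.
- Section 11.8: on the Table 1 schedule the first three follow-up visits are 2, 6 and 12 weeks. The 12-week window closes at 12 × 7 + 14 = day 98. Taking 2 years as day 730, that is 730 − 98 = 632 days before the endpoint. Day 98 is the earliest bound: all contact attempts must also have failed.
- On the shorter visit list in section 10.6, the first three would be 2 weeks, 6 weeks and 1 year, and the last would close at 365 + 90 = day 455. The earliest closure therefore depends on which schedule a site follows.

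**4. What the two windows change.**

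- Table 1: 730 ± 60 = days 670 to 790, which is 121 days.
- Section 10.6: 730 ± 90 = days 640 to 820, which is 181 days.
- A form dated on one of the 181 − 121 = 60 days between (640 to 669, or 791 to 820) is in window under section 10.6 and out of window under Table 1. No passage removes an out-of-window form from the analysis.

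**5. What bias could look like.** This is an illustration only. Let a fraction f lack a 2-year score and improve by m on average, while completers improve by 31.4 (the section 16.1 figure, which that section ties to one year). The all-subject mean is (1 − f) × 31.4 + f × m.

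| f | m = 0 | m = 10 | Completers |
|---|---|---|---|
| 25% | 23.6 | 26.1 | 31.4 |
| 40% | 18.8 | 22.8 | 31.4 |

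With m = 0 the all-subject mean falls to 18.0 at f = 1 − 18.0 / 31.4 = 43%. Both f and m are assumptions. The documents state neither how many subjects would be closed early nor how they would have fared, and f here covers every cause of a missing score.

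**The case against.** **Section 11.8 does not close a subject merely for missing forms.** A reader might infer that missing the 2-, 6- and 12-week contacts is enough. It is not: all contact attempts must also fail, or the subject must choose to leave. This stands, and it limits how many of the values forgone under section 11.8 were truly obtainable. It does not apply to section 12.4.4, which has no such condition.

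**Sections 11.8 and 12.4.5 need not contradict each other outright.** A reader might take section 12.4.5 to forbid closure before the 2-year point. Its wording can also mean failing to complete the series of questionnaires that runs to 2 years, and section 12.4.8 lists loss to follow-up among the ways participation ends other than at the 2-year visit. Both rules are permissive. This stands: the sections differ in trigger and contact steps and need aligning, but a flat contradiction is only one reading.

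**The window conflict has a tie-breaker.** Section 11.7 points to Table 1, and nothing excludes late or early scores. This stands. It would be wrong to say that the window conflict makes primary data missing.

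**The sample is ample.** This also stands, as step 2 shows. It answers a concern about power but not one about bias.

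**Conclusion.** The point holds in limited form. Section 12.4.4 is the clearest problem: it allows a reachable, consenting subject to be removed for poor questionnaire compliance, although the primary endpoint is itself a questionnaire collected remotely. Section 11.8 adds a weaker version of the same risk, for subjects unreachable as early as about day 98. In both cases an obtainable 2-year score may be forgone and the single-arm mean may be biased. The re-entry provision in section 12.4.4 is written for subjects who chose to withdraw, so it does not clearly cover those removed by a site.

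The size is unknown. The figures in step 5 show only how bias would scale under assumed values, and they do not predict it. The documents do not support a claim of inadequate power.

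The differences between section 10.6, Table 1 and the synopsis are inconsistencies to correct. They leave unclear which scores count as on time, but they do not create missing data.

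**What to change.** - **Section 12.4.4:** remove questionnaire non-compliance as a ground for study withdrawal, and say that missed questionnaires do not count as the protocol non-compliance that remains in the sentence. Leave consent withdrawal and medical discretion unchanged.
- **Sections 11.8 and 12.4.5:** state one rule in both, so that a subject who has not withdrawn consent is still contacted for the 2-year score before being closed as lost.
- **Section 10.6:** use the visits and the 1- and 2-year window of Table 1, and reconcile the enrolment period with the synopsis.
- **Section 16:** state that 2-year scores collected outside the window are included in the primary summary, with an in-window summary alongside.

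The cost is an amendment to the wording of these sections (with the IRB approval that section 20 requires), a few more remote contact attempts by site staff, and one extra summary.

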10.7 Primary and Secondary Endpoint

The study device is intended to relieve pain and restore function in patients with adequate quality and quantity of bone stock to support the prosthesis. The objective of this PMCF study is to confirm the long-term safety, performance and clinical benefits of the AccuFill® and SCP® Surgical Instrumentation in patients with at least one bone marrow lesion in the hip.

10.7.1 Primary Endpoint

The primary endpoint is defined by the overall group mean improvement from baseline of the Modified Harris Hip Score at the two year time point. The safety of the system will be assessed by monitoring the frequency and incidence of adverse events. Relation of the events to implant (Accufill®), instrumentation (SCP® Surgical Instrumentation) and/or procedure should be specified.

10.7.2 Secondary Endpoint

The secondary endpoint is defined by the functional performance and clinical benefits of the study device and is assessed by:

- Pain and functional performance will be measured by the Numeric Pain Scale and Modified Harris Hip Score
- Subject quality-of-life will be measured by the EQ-5D-5L.

10.8 Financing of the Study

Funding for this clinical study is made available by Zimmer Biomet to support clinical data collection, IRB review fees and other expenses associated with the conduct and execution of this study protocol as outlined in the fully executed Clinical Trial Agreement.

Zimmer Biomet will provide each investigative site with Investigator Binder including the protocol, paper copies of case report forms and logs, study tools, and subject stipend cards. The Zimmer Biomet Study Representatives are available to provide additional supplies upon request.

10.9 Definition of Completion of the Study

The study will be completed when all enrolled subjects have completed all follow-up visits.

11 Study Procedures

11.1 Offer of Study Participation

For each consecutive patient presenting as a study candidate for the SCP procedure, study participation shall be offered based on the indications and patient selection factors contained in the Information for Use (IFU). Based on the patient's response, the patient may be invited to enroll in the clinical study.

11.2 Informed Consent

All study subjects are required to undergo the process of Informed Consent and sign an Institutional Review Board (IRB) approved Informed Consent Form, compliant with 21 CFR Part 50-Protection of Human Subjects, and in accordance with institutional policies. Failure to obtain and properly document this process is in violation of the US Code of Federal Regulations, the Declaration of Helsinki, and this study protocol.

Two copies of the informed consent will be made and distributed as follows: (1) the original of the signed informed consent will be kept in the subject's file at the study site and (2) a copy will be provided to the subject.

11.3 Determination of Eligibility and Enrollment

Potential subjects will be screened from each Investigator's patient population to determine if they meet the inclusion criteria described in Section 7.1 and none of the exclusion criteria described in Section 7.2. Subjects will not be invited to participate in the study until after approval of the protocol by the reviewing IRB.

Subjects will be considered enrolled in the study if they meet the eligibility criteria, consent to participate in the Investigation and undergo the SCP Procedure where AccuFill is injected. Valid enrollment status is not granted until after surgery due to the possibility of intra-operative exclusions where the SCP Procedure does not occur. At the conclusion of the subject's surgery, the subject will be entered into the electronic database and a subject number will be generated.

Retrospective enrollment will only be allowed with prior written approval from the Sponsor after evaluation of pre-operative data available for potential retrospective subjects. The subject will sign an Informed Consent Form prior to completing follow-up study questionnaires.

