7.3 Compatibility

To determine whether devices have been authorized for use in a proposed combination with Zimmer and/or Biomet products, please contact your sales representative or visit the Zimmer Electronic Labeling Service (eLabeling) website: <https://labeling.zimmerbiomet.com/>

8 Study Population

Approximately 50 subjects, each with at least one subchondral bone defect in the form of a cyst and/or bone marrow lesion (BML), insufficiency fracture or bone defect associated with early stage avascular osteonecrosis (AVN) in the femoral head, femoral neck and/or acetabulum who have elected to undergo or who have undergone the Subchondroplasty Procedure, will be enrolled in the study.

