11.4 Baseline/Pre-operative Assessment

All pre-operative procedures are to be completed prior to the study surgery. The Schedule of Events is listed in Table 1.

The pre-operative visit will include collection of basic demographic information, medical history, hip history and current use of prescription and over-the-counter pain medication and therapies.

The subject is to complete a series of surveys and scales regarding their clinical outcomes at the time preceding surgery, including pain, stiffness, function, and activities. These scales include:

- Numeric Pain Scale
- Modified Harris Hip Score
- Hip Outcome Score
- EQ-5D

For subjects enrolled after the completion of the Subchondroplasty Procedure, basic demographic information, medical history, hip history and pre-operative use of prescription and over-the-counter pain medication and therapies data should be collected, if available, from the subject's medical record or via patient interview. Pre-operative Numeric Pain Scale, Modified Harris Hip Score, Hip Outcome Score, and/or EQ-5D should **only** be entered if they were collected as part of the standard of care

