16.1 Sample Size Calculation

The sample size required is based on the overall group mean improvement of the Harris Hip Score by at least the minimal clinically important differences (MCID) of 18.0 points from baseline to one year.

Based on internal Zimmer Biomet studies, assuming an improvement from baseline of 31.4 points with a standard deviation of 22.4, 80% power and alpha set at 0.05, 24 patients are needed to show the mean improvement from baseline is greater than the MCID of 18.0. Considering an attrition rate of 25%, 32 patients should be enrolled in the study. At an enrollment rate of approximately 50 subjects the study is more than adequately powered to show improvement over the MCID.

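### Retrospective enrolment is not reconciled with the prospective consecutive design, requires no baseline score, and has no separate analysis

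*Combined protocol and SAP*

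**What the plan says.** Section 10.6 calls the study prospective and states: "To reduce bias, a consecutive subject series will be recruited". Section 10.5 gives avoidance of selection bias as the reason for approaching every consecutive patient. Section 12.4.1 places the offer at the pre-operative visit.

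The synopsis (Section 4) and Section 8 define a wider population, namely patients "who have elected to undergo or who have undergone the Subchondroplasty Procedure, will be enrolled in the study". Section 11.3 sets the condition for those already operated on: "Retrospective enrollment will only be allowed with prior written approval from the Sponsor after evaluation of pre-operative data available for potential retrospective subjects". They sign consent before completing follow-up questionnaires. Under Section 11.4 their pre-operative scores, including the Modified Harris Hip Score, are entered only "if they were collected as part of the standard of care".

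The primary endpoint (Section 10.7.1) is the mean change in Modified Harris Hip Score from baseline to two years. Adverse-event frequency appears in the same section. Conversion (Section 10.4) or revision (Section 11.9) ends participation. Section 16.3 plans descriptive summaries with 95% confidence intervals. It allows strata and gives sex and body mass index as examples; enrolment type is not mentioned.

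**The concern.** The consecutive pre-operative offer is the safeguard against selection that the plan names, and it does not cover the retrospective route. For that route the plan sets no cap, no limit on time since surgery, no rule that past cases be taken consecutively, no rule that approval be made without knowledge of the post-operative course, and no separate analysis.

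Three results could be affected.

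- **Primary endpoint, availability.** Section 11.3 has the sponsor look at the pre-operative data but does not make a score a condition of approval. Section 11.4 does not say whether the 60-day window in Table 1 applies to standard-of-care scores. A subject with no baseline has no change score but still fills one of the 50 places.
- **Conversion and adverse events.** A hip already converted has no follow-up to give, so a retrospective subject has in effect survived event-free to consent. Section 10.5 bars data collection before consent, and the items that Section 11.4 recovers for these subjects do not include adverse events. Early events can go uncounted while the subject stays in the denominator.
- **Primary endpoint, size.** If better responders among unconverted patients are the ones proposed, the mean change is inflated.

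**Working it through.** **1. The plan's own figure (Section 16.1).** Inputs: "assuming an improvement from baseline of 31.4 points with a standard deviation of 22.4", threshold 18.0, "80% power and alpha set at 0.05". Sidedness is not stated.

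- Difference to detect: 31.4 − 18.0 = 13.4.
- Two-sided one-sample t-test (noncentral t): n = 24, power 80.1%. The two-sided normal approximation gives 21.9, so 22; a one-sided t-test gives 19. The stated 24 therefore matches the two-sided t-test.
- With 25% attrition: 24 / 0.75 = 32, as stated.
- At 50 enrolled: 50 × 0.75 = 37.5, so 37 evaluable, power 94.3%.

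The arithmetic is sound. The calculation is for the Harris Hip Score at one year; I carry the 24 over to the two-year endpoint because the plan gives no other requirement.

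**2. Missing baselines.** The retrospective share and the proportion lacking a score are not given. If k of the 50 lack a baseline and 25% of the rest are lost, evaluable n = (50 − k) × 0.75.

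| k | Evaluable | Against 24 |
|---|---|---|
| 0 | 37.5 | above |
| 15 | 26.25 | above |
| 18 | 24.0 | equal |
| 19 | 23.25 | below |
| 25 | 18.75 | below (power 67% at n = 18) |

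The 15 and 25 are assumptions, and having no baseline in any retrospective subject is the worst case.

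**3. Conversion.** The only failure rate in the document is for the knee, 30% at two years (Section 6.1). Assume it applies, with a constant hazard.

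- h = −ln(0.70)/2 = 0.178 per year.
- Converted by 6 months: 1 − exp(−0.5h) = 8.5%. By 12 months: 1 − exp(−h) = 16.3%.
- Conversion by year 2 among those entering unconverted at 12 months: 1 − exp(−h) = 16.3%. At 6 months: 1 − exp(−1.5h) = 23.5%.
- Pooled rate with retrospective share r: (1 − r) × 30% + r × (16.3% or 23.5%).

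| Retrospective share | Entry at 12 months | Entry at 6 months |
|---|---|---|
| 10% | 28.6% | 29.3% |
| 30% (15 of 50) | 25.9% | 28.0% |
| 50% | 23.2% | 26.7% |

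If the true rate were 10%, the same steps give 5.1% and 7.6% in the retrospective group. At a 30% share the pooled figures are 0.7 × 10 + 0.3 × 5.1 = 8.5% and 0.7 × 10 + 0.3 × 7.6 = 9.3%.

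**4. Mean two-year change.** This depends on how converters are analysed, which the plan does not say.

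- *Observed scores only:* prospective converters are withdrawn and also give no two-year score. Exclusion of past converters then adds no bias by itself.
- *Converters scored as zero improvement, 31.4 points below the others:* at a 30% share the upward bias is 31.4 × 0.3 × (0.300 − 0.163) = 1.3 points (12-month entry), or 31.4 × 0.3 × (0.300 − 0.235) = 0.6 points (6-month entry).
- *Selection of better responders:* size unknown. For scale, at n = 37 and SD 22.4, an upward bias of 1 or 2 points raises the chance that the lower 95% limit falsely exceeds 18.0 from 2.5% to 4.5% or 7.6%.

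**The case against.** A reader might infer that the sponsor picks patients known to be doing well. The text does not say so: the approval criterion in Section 11.3 is pre-operative data, no section has outcomes reviewed, and none bars a converted patient. What stands is the absence of a rule. Whoever proposes a past case may know its early course, and nothing brings past failures in.

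A reader might also infer that pooling necessarily raises the mean change. It does not. Under an observed-score analysis the exclusion of converted hips is common to both routes.

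The sponsor's review could screen out patients without a baseline, and standard-of-care scores may well fall within 60 days. Both are possible, but neither is required. Even with 15 missing baselines, about 26 evaluable exceeds 24, so loss of power is not established.

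Conversion is not a listed endpoint and no time-to-event analysis is planned, which limits the weight of the conversion figures. Conversion is nevertheless screened for throughout (Section 10.4), and adverse-event frequency does sit under the primary endpoint. Medical records are permitted sources (Section 12.2.5), so early events could be recovered, but Section 11.4 does not ask for this.

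**Conclusion.** The contradiction between Sections 10.5, 10.6 and 12.4.1 and Sections 4, 8, 11.3 and 11.4 is real and unreconciled. Two consequences follow from the plan as written: retrospective subjects may lack the primary change score while counting toward the 50, and their surgery-to-consent time is in effect event-free, so pooled conversion and early adverse-event frequencies can be understated. An inflated mean change is possible but not shown.

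The actual size cannot be computed, because the share and timing of retrospective enrolment are not given. With 15 of 50 retrospective, the knee rate and a constant hazard, pooled conversion is understated by about 2 to 4 percentage points. Evaluable numbers fall below 24 only if 19 or more of the 50 lack a baseline. The sample-size calculation itself is not at fault. The point deserves correction because the remedy is cheap, not because a large bias has been demonstrated.

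**What to change.** Reconcile Sections 10.5, 10.6 and 12.4.1 with Sections 4, 8, 11.3 and 11.4: either delete the retrospective route, or describe the study as mixed prospective and retrospective.

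If the route is kept:

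- **Section 11.3:** require a documented pre-operative Modified Harris Hip Score within the Table 1 window (no more than 60 days before surgery); have approval decided without post-operative outcome data; and require an offer to all consecutive past cases at the site, including converted ones, with a sentence on how a hip already converted at consent is recorded.
- **Section 16.3:** report the primary endpoint, adverse events and conversions by enrolment type, with a prospective-only analysis of the primary endpoint. In any conversion rate, count retrospective subjects at risk only from consent; list conversions before consent separately.
- **Patients not enrolled:** keep non-identifying counts only, because Section 12.4.1 excludes collecting data on candidates who do not consent.

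Retrospective subjects with a valid baseline need not be barred from the pooled primary analysis, provided the prospective-only result stands beside it.

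Cost: amended wording, a simple tally, a little more analysis and somewhat fewer eligible retrospective subjects. No new patient assessments are needed.
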